5. Lack of appetite, nausea, vomiting
6. Dyspnea
7. Headache, pain in the chest, bone pain
8. Priapism
9. Increase/decrease blood pressure
10. Anaphylactic reactions/erythema

Risks for blood draw:

- Occurrence of discomfort and/or a bruise at the site of puncture
- Less commonly, fainting
- The formation of a clot or swelling in the vein and surrounding tissue
- Bleeding from the puncture site
- On rare occasions an infection may develop at the site where the blood is collected

Potential Risks of No Treatment

Since Omegaven® will only be offered to those patients for whom no standard therapy has been safe and effective, the risks of not being treated are those allowing for the natural history of their disease and associated clinical manifestations to progress. These include fulminate liver failure and death.

VII. Overall Risk Assessment

Patients will be at some risk inherent in taking a pharmaceutical agent that has not been fully evaluated for long duration treatment. However, the availability of safety data demonstrates no life-threatening risks or toxicities to vital organs or physiologic functions. The potential benefits of Omegaven® in this patient population are mainly based on human trials and our own experience.

VIII. Risk Category

The research involves greater than minimal risk, but presents the prospect of direct benefit to the individual subjects.

IX. Methods

A. Subject Selection

No concomitant medications will prohibit enrollment.

Inclusion Criteria

1. Males and females ages one month of age to 18 years of age
2. Patients with intestinal failure on TPN
3. Patients who have a conjugated or direct bilirubin of ≥ 3 mg/dl for more than 4 weeks and in whom other causes of cholestasis have been excluded with reasonable certainty utilizing biochemical, serologic, microbiologic, and radiographic techniques. Liver biopsy is not required to rule out other disorders, but may be utilized at the clinician's discretion
4. Patients in whom reduction of IV soy-based lipid load to an **average** <1.2 g/kg body weight/day has failed to reduce the conjugated or direct bilirubin within ≥ 30 days of implementation

5. Willing to use birth control during study participation for females of child-bearing potential, as determined by investigator.
6. Signed informed consent for use of Omegaven® obtained

Exclusion Criteria

1. Any of the contraindications to use of Omegaven®

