The primary endpoint will be reduction in conjugated or direct bilirubin level to below 1 mg/dl. Data from previous retrospective analyses and prospective uncontrolled studies suggest that from the inception of Omegaven® therapy, conjugated or direct bilirubin will remain elevated for approximately 8 weeks at levels comparable to those observed prior to administration of Omegaven®. Subsequently, levels are expected to fall by approximately 1 mg/dl/week until they normalize. The time to normalization will vary according to each patient's baseline conjugated or direct bilirubin level. Thus, a patient who begins Omegaven® with a conjugated or direct bilirubin level of 7 mg/dl is likely to experience normalization within 14 weeks (8+6 weeks). We will compare the group receiving Omegaven® with historical controls from our internal registry who have demonstrated cholestasis while on Intralipid®. We will compare changes in conjugated/direct bilirubin concentration over time between groups via Kaplan-Meier analysis (see Statistics section XIII).

Secondary endpoints will be: normalization of total bilirubin and liver enzymes. Differences in these values at the end of 14 weeks of therapy will be compared with those of controls via Kaplan-Meier analysis identical to that employed for conjugated and direct bilirubin levels. Furthermore, we expect that elevated triglyceride levels which might be present at the initiation of therapy will have normalized at the same time that liver profiles have normalized.

XI. Assessment of Safety/Data Safety Monitoring Board

A DSMB will monitor the study for the occurrence of adverse events (both serious and otherwise). A significant increase in the rate of adverse events would be cause for concern for the safety of participants in the study. Information on adverse events will be presented in several ways: (1) listings of serious adverse events with accompanying narrative summary by the PI; (2) summaries of adverse events by body system and type of event. This information will be presented to the DSMB.

The DSMB will also monitor the efficacy and the conduct of the study. Interim monitoring reports for the DSMB will include, but will not be limited to, such tabulations as:

1. platelet counts
2. essential fatty acid profiles
3. coagulation studies
4. liver profiles

5. renal profiles

The DSMB will meet at least once per year and possibly more frequently given the expected speed of recruitment and study medication administration.

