All adverse events will be followed until they are resolved or the patient's participation in the treatment ends (i.e., until a final report is completed for that patient).

In addition, all SAEs and those non serious events assessed by the Investigator as attributable (i.e. possibly, probably, definitely related to the drug) will continue to be followed even after the patient's participation in the treatment is over. Such events will be followed until they resolve or until the Investigator assesses them as "chronic" or "stable." Resolution of such events is to be documented in the CRF.

XIII. Statistics

We selected a study number of 25 patients (5 patients a year for 5 years) even though, statistically, a number of 19 will be satisfactory based upon power analysis. We know from our current registry that 10% of historic controls will experience resolution of cholestasis within 8 weeks while receiving Intralipid®, and we know from the data of Gura, et al (5) that approximately 50% of experimental subjects will experience resolution of cholestasis within eight weeks while receiving Omegaven®. Thus, achieving an alpha of 0.05 and a beta of 0.80, a sample size of 19 patients and 19 controls will be adequate (11). However, insofar as this is a compassionate release protocol, we will not refuse entry into the study even if we have shown statistically that Omegaven® is efficacious. We estimate that at most we will acquire five patients per year, and we anticipate that within five years, Omegaven® or SMOF (soy, MCT, olive oil and fish oil) parenteral lipids will have obtained FDA approval for clinical use.

The analysis populations will include (1) subjects receiving Omegaven® under this protocol and (2) historical controls from our internal registry who have demonstrated cholestasis while on Intralipid®. Paired t-tests will be used to report the statistical significance of differences between means. A p value of 0.05 or less will be considered significant. Wilcoxon Tests will be used to report the statistical significant differences between medians, and χ^2 tests/Fisher's exact tests will be used to report proportions. A Kaplan-Meier analysis will compare changes in conjugated/direct bilirubin concentration over time between groups. Cox proportional hazard models will be used to estimate crude and adjusted hazard ratios. Analyses will be performed via SAS 9.2 (SAS Institute Inc, Cary, NC) and S-Plus 8.1.1 (Insightful, Inc, Seattle, WA).

IX. Data Management

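### Sections X and XIII give incompatible expectations for Omegaven at 8 weeks, and the power statement rests on the 8-week figure

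*Combined protocol and SAP*

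**What the plan says.** Section XIII takes its sample size from two proportions at 8 weeks. For controls, "10% of historic controls will experience resolution of cholestasis within 8 weeks while receiving Intralipid". For treated patients, "approximately 50% of experimental subjects will experience resolution of cholestasis within eight weeks while receiving Omegaven", a figure attributed to reference 5. With alpha 0.05 and a stated 0.80 (called beta, evidently meaning power), it concludes that 19 per group is enough. It then plans for 25 treated patients, at five a year for five years.

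Section X defines success without a time limit: "The primary endpoint will be reduction in conjugated or direct bilirubin level to below 1 mg/dl". It then describes the expected course on Omegaven, citing previous retrospective and uncontrolled prospective data: "conjugated or direct bilirubin will remain elevated for approximately 8 weeks at levels comparable to those observed prior to administration of Omegaven". After that, "Subsequently, levels are expected to fall by approximately 1 mg/dl/week until they normalize". Its worked example is a patient starting at "7 mg/dl is likely to experience normalization within 14 weeks (8+6 weeks").

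Section IX.A sets the entry level: "Patients who have a conjugated or direct bilirubin of ≥ 3 mg/dl for more than 4 weeks".

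The main comparison with historical controls is by Kaplan-Meier, with Cox models for hazard ratios. For the secondary endpoints Section X names week 14: "Differences in these values at the end of 14 weeks of therapy will be compared with those of controls via Kaplan-Meier analysis".

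**The concern.** Both sections describe the same drug over the same first 8 weeks. One expects half the treated group to have resolved by then. The other expects the typical patient to have hardly changed. A sponsor cannot hold both expectations.

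It matters because the 8-week contrast is the only basis given, in the text supplied, for saying that 19 patients would suffice. If Section X is right, the power statement refers to a time when little or no treatment effect is expected. If Section XIII is right, Section X misdescribes the expected course, and readers of the efficacy section are given the wrong time frame. Either way, the stated 80% cannot be relied on until the two are reconciled.

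**Working it through.** **1. Reproduce the plan's figure.** Inputs from Section XIII: control proportion 0.10, Omegaven proportion 0.50, alpha 0.05, power 0.80. Two-sided testing and independent groups of equal size are assumed, because the plan states neither sidedness nor any matching. (Reference 11 concerns matched designs, but no within-pair correlation is given.)

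- Pooled two-proportion formula, with mean proportion 0.30: n = [1.96 × √(2 × 0.30 × 0.70) + 0.842 × √(0.10 × 0.90 + 0.50 × 0.50)]² / 0.40² = (1.270 + 0.491)² / 0.16 = 19.4 per group.
- Arcsine formula: n = 2 × (1.96 + 0.842)² / [2 × (arcsin √0.50 − arcsin √0.10)]² = 15.70 / 0.860 = 18.3 per group, which rounds up to 19.
- Normal-approximation power at 19 per group: 79.2%.

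The stated 19 is therefore about right for its inputs.

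**2. Work out what Section X implies.** Inputs: a plateau of about 8 weeks, then a fall of about 1 mg/dl per week, to a threshold of 1 mg/dl.

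Typical time to threshold in weeks = 8 + (baseline − 1) / 1.

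| Baseline (mg/dl) | Typical time to 1 mg/dl | Weeks after week 8 |
|---|---|---|
| 3 (lowest eligible) | 8 + 2 = 10 | 2 |
| 5 | 8 + 4 = 12 | 4 |
| 7 (Section X's example) | 8 + 6 = 14 | 6 |

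**3. Set the two side by side.** Keep Section X's rate of fall and ask how short the plateau must be for a patient to reach the threshold by week 8. The answer is 8 − (baseline − 1) weeks: 6 weeks from a baseline of 3, 4 weeks from 5, and 2 weeks from 7. Section XIII needs this, or something equivalent, in about half the group. Section X gives about 8 weeks for the plateau.

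**4. Look for a reconciliation.** Section XIII gives no definition of resolution that differs from the endpoint in Section X. A looser threshold would not help, because Section X expects levels comparable to pre-treatment throughout those weeks. The Background's summary of the reference 5 trial (18 children) reports resolution but gives no time to it. Nothing else in the supplied text bridges the gap.

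**The case against.** The strongest reply is that Section X speaks of approximate values and a typical course, and gives an upper bound (within 14 weeks) in its example. Some patients will resolve sooner, and for a patient at the 3 mg/dl floor the gap is only about 2 weeks. That stands for individuals. It does not stretch to half the group, since 3 mg/dl is the lowest baseline allowed and the gap widens with every higher one.

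A second reply is that Section XIII names its sources, the internal registry and a published trial, and may be the correct section. That also stands. A reader might infer that the 8-week figure is the faulty one, but the documents do not establish this. Section X rests on earlier data too, and neither set of data can be seen here.

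A third reply is that nothing operational hangs on the number. The target of 25 exceeds 19 and follows expected accrual, entry will not be closed once efficacy is shown, and under Section IV treatment can run well beyond week 8. This is correct and limits the consequence. It does not rescue a power statement whose main input is contradicted elsewhere in the same protocol.

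A reader might also infer that the trial is underpowered. The documents do not support that. The planned Kaplan-Meier and Cox comparison is not confined to week 8, no power is stated for it, and no proportions at later times are given from which to calculate it. Nor is there a calculation error: whether the result is 19 or 20 depends only on the formula chosen.

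**Conclusion.** The concern holds as an internal inconsistency. Section XIII's 50% resolved by week 8 and Section X's plateau of about 8 weeks cannot both be the expectation. On Section X's figures the typical patient reaches the endpoint 2 to 6 weeks after the time point used for power, for baselines of 3 to 7 mg/dl, and later still for higher baselines.

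This rests on reading resolution in Section XIII as the Section X endpoint, or at least as a material fall in bilirubin, and on taking Section X's plateau and slope as the typical course. Which section is right cannot be settled from the documents. The stated 80% power should be treated as unconfirmed until they agree. It should be corrected, but it gives no reason to change the enrolment target or the analysis.

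**What to change.** Reconcile Sections X and XIII, by one of two routes.

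- **If Section X holds:** replace the 8-week basis in Section XIII with control and Omegaven proportions at one common later time point consistent with Section X. Week 14 is a natural candidate, since Section X already uses it for the secondary endpoints. On Section X's course, only patients starting at about 7 mg/dl or below would typically have reached the endpoint by then, so the Omegaven proportion should reflect the expected spread of baselines. Take the control proportion from the registry and the Omegaven proportion from the cited data.
- **If 50% by 8 weeks holds:** correct the expected course in Section X, including its worked example.

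In both cases, restate the power for 25 treated subjects and the actual number of registry controls, and name the test to which it applies. Power for a comparison of proportions at one time point is not power for the Kaplan-Meier or Cox comparison, and the text should say which is meant. Write power of 0.80 where the text now says beta.

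The cost is a protocol wording change, a registry query and a re-reading of the cited Omegaven data. The stated power may become less favourable. No extra patients are needed and the planned analysis is unchanged.

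### Section XIII sizes the historical comparison at one registry control per treated child and gives no rule for which, or how many, registry children with already known outcomes will be analysed

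*Combined protocol and SAP*

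**What the plan says.** Section XIII (Statistics) rests the sample size on two rates. For controls: "We know from our current registry that 10% of historic controls will experience resolution of cholestasis within 8 weeks" on Intralipid. For treated children, from a cited study: "approximately 50% of experimental subjects will experience resolution of cholestasis within eight weeks". With "achieving an alpha of 0.05 and a beta of 0.80" (the 0.80 must be meant as power), it concludes that "a sample size of 19 patients and 19 controls will be adequate". The method cited, reference 11, is a power calculation for matched case-control studies. The plan then enrols 25 treated children rather than 19, at an expected maximum of five a year.

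The control analysis population is described in Sections X and XIII only as past patients in the site's own registry who were cholestatic while receiving Intralipid. No bilirubin threshold, calendar period, index date, matching rule, number or cap is given, and nothing says that all such children will be used. For the analysis, Section XIII names chi-square or Fisher's exact tests for proportions, paired t-tests and Wilcoxon tests, Kaplan-Meier and Cox models, and adds: "A p value of 0.05 or less will be considered significant".

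**The concern.** There is no concurrent control arm, so all the comparative evidence on efficacy depends on which registry children are put beside the treated ones. Their outcomes are on file, and the sample-size paragraph quotes their resolution rate. With no rule for entry, knowledge of outcome can influence the choice of records, even without intent, and a reader of the results could not rule that out.

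The second issue is efficiency. Treated children arrive slowly, whereas controls are existing records. A calculation at one control per child leaves unused whatever further precision the registry could supply. If the analysis did stop at about 19 controls, Fisher's test would fall short of the 80% target even with 25 treated children.

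**Working it through.** **Inputs.** From Section XIII: control rate 0.10, treated rate 0.50, alpha 0.05, power 0.80, 19 and 19 in the calculation, 25 treated planned. Sidedness is not stated; two-sided is assumed because it reproduces the plan's figure. The number of eligible registry controls is not in the documents, so a range is shown.

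**1. The plan's own figure.** The odds ratio is (0.5/0.5)/(0.1/0.9) = 9. In the cited matched method with one control per patient and no within-pair correlation:
- Probability of a discordant pair: 0.5×0.9 + 0.5×0.1 = 0.5.
- Null mean 0.5×1/2 = 0.25 and variance 0.5×1/4 = 0.125.
- Alternative mean 0.5×9/10 = 0.45 and variance 0.5×9/100 = 0.045.
- n = (1.960×√0.125 + 0.842×√0.045)² / (0.45 − 0.25)² = 18.99, so 19 pairs.

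The stated 19 and 19 therefore reproduces. The pooled two-proportion formula for independent groups gives 20 per group.

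**2. Power against the number of controls.** For independent groups, power is the sum, over all outcomes (a resolved of n treated, b resolved of m controls), of Bin(a; n, 0.5)×Bin(b; m, 0.1), counting only outcomes that the test declares significant at two-sided 0.05. This was enumerated exactly for two tests that Section XIII allows.

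| Treated | Controls | Fisher | Uncorrected chi-square |
|---|---|---|---|
| 19 | 19 | 70.9% | 81.5% |
| 19 | 38 | 89.7% | 92.7% |
| 25 | 12 | 61.3% | 74.8% |
| 25 | 19 | 78.0% | 85.8% |
| 25 | 25 | 83.3% | 91.1% |
| 25 | 50 | 95.6% | 97.1% |
| 25 | 100 | 98.5% | 99.1% |

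With the planned 25 treated, going from 19 to 50 controls adds 17.6 percentage points by Fisher (95.6 − 78.0) and 11.3 by chi-square (97.1 − 85.8). From 50 to 100 the gain is 2.9 and 2.0 points.

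**3. Sensitivity to the treated rate.** Section X expects bilirubin to stay near its starting level for about the first 8 weeks and to fall only afterwards. Section XIII assumes that half the treated children have resolved by 8 weeks. The two do not sit together, so the 50% may be too high for that time point. If it were 40% (an assumption, for illustration), Fisher power with 25 treated would be 53.7% with 19 controls, 59.1% with 25, 81.1% with 50 and 86.7% with 75. The number of controls matters more when the effect is smaller than planned.

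**4. Selection.** No calculation applies. Section XIII gives a known registry outcome rate, and neither Section X nor Section XIII gives an entry rule beyond cholestasis on Intralipid. Treated children, by contrast, must meet Section IX.A: conjugated or direct bilirubin of at least 3 mg/dl for more than 4 weeks, and failure of soy-lipid reduction. Nothing requires the same of controls.

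**The case against.** A reader might infer that the plan restricts the analysis to 19 controls, and that using every eligible control would lift power from 71% to about 90%. The documents do not support either part.

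- The 19 is the minimum from a power calculation. The same sentence's 19 patients is plainly not a limit, since 25 will be enrolled, and the control population carries no cap. The plan could be read as already intending to use all such children.
- The 71% pairs the least favourable of the named tests with the minimum number treated. Chi-square reaches 81.5% at 19 and 19, and Fisher reaches 83.3% at 25 and 25.
- The 90% needs 38 controls, a number found nowhere in the documents. If the treated children's entry criteria were applied to the registry, fewer than 19 might qualify.

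Other objections also have force. The cited method and the paired t-tests suggest that matching may be intended, in which case an unmatched power figure is only a guide. The main comparison is by Kaplan-Meier and Cox models, whose power is not computed here. That additional controls cost only record extraction is a reasonable inference from their being in an internal registry, but it is not stated. More controls narrow the interval around an estimate that may still be biased.

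What these objections leave standing is the missing rule. If 19 is not a cap, the control set is simply open, and the outcomes are known.

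**Conclusion.** The point holds as a gap in specification: the only control number is a 1:1 minimum, and the plan does not say which or how many registry children will be analysed, although their outcomes are known. With 25 treated and the plan's 50% versus 10%, Fisher power runs from 78% with 19 controls to 98% with 100 (chi-square 86% to 99%), and falls to 61% by Fisher with 12. These figures assume independent groups, a two-sided 0.05 test, the plan's two 8-week rates and control numbers that the documents do not supply.

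A reader might also infer that using all the controls would by itself remove the choice of which outcomes to include. It would not. Eligibility, period and index date could still be tuned to control outcomes already seen unless they are set first and without reference to outcome. Confounding and era bias would remain in any case.

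**What to change.** Amend Section XIII to state that:
1. Control eligibility, calendar period and index date are fixed without reference to outcome. Eligibility should follow the treated children's bilirubin and failed-lipid-reduction criteria in Section IX.A, as far as the registry records them.
2. Every registry child who meets these criteria is analysed, with no sampling. If matching is intended, say so, give the matching variables, and use all eligible matches for each treated child.
3. The resulting number of controls is stated, and power is restated for that number, for 25 treated and for the test that will be used.
4. The 50% resolution by 8 weeks is reconciled with the time course in Section X before power is restated.

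The cost is extraction of additional registry records and a short amendment. No further patients or procedures are needed.

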PNAC is a potentially fatal disorder, and the consequences are heinous if the process cannot be reversed. In Omegaven® we have an agent that is potentially life saving, and its use in hundreds of patients has shown little if any toxicity. After ongoing controlled trials of Omegaven® are completed, the agent will be evaluated for approval by the FDA. Until such time as FDA approval is granted, we will be unable to administer Omegaven® without requesting approval for compassionate use. The IRB granted approval for protocol 2009-1041, and this protocol will call for even stricter inclusion criteria. Therefore, we seek IRB approval for this study.

IV. Duration of Study

Once IRB approved, enrollment of subjects into this study will occur for up to 9 years. Subjects will receive Omegaven at a dose of up to 1 g/kg body weight/day until they no

longer require TPN or until their conjugated or direct bilirubin has normalized and their enteral lipid intake is sufficient to discontinue intravenous lipids.

A total study duration of 10 years is anticipated to complete the study (enrollment, analyses, and report writing).

V. Potential Benefits

The use of Omegaven® has the potential to benefit patients with PNAC by facilitating the resolution of cholestasis.

VI. Potential Risks of Omegaven® Treatment

Omegaven® has been studied in animal pre-clinical models as well as Phase I, II, III, and post marketing human trials in both Europe and Asia. Prolonged bleeding time and an inhibited platelet aggregation can occur. It should not be administered to patients known to be allergic to fish or egg protein.

Contraindications to Omegaven® include the following:

1. Impaired lipid metabolism
2. Severe hemorrhagic disorders
3. Unstable diabetes mellitus
4. Collapse and shock
5. Stroke/Embolism
6. Recent cardiac infarction
7. Undefined coma status

Side Effects:

Risks of Omegaven®

The infusion of Omegaven® can lead to a prolonged bleeding time and an inhibited platelet aggregation. In rare cases, patients may experience a fishy taste.

The administration of Omegaven® should be stopped or reduced if there is a marked increased in blood glucose levels during the Omegaven® infusion. Undesirable effects that are seen during the infusion of Omegaven® that may also occur with conventional fat emulsions (i.e., Liposyn® or Intralipid®) include:

1. Slight rise in body temperature
2. Heat sensation and/or cold sensation
3. Chills
4. Flushing or cyanosis

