 - Impaired lipid metabolism (triglycerides >1000 mg/dL) while on 1g/kg/day or less of Intralipid
 - History of severe hemorrhagic disorders (ie. hemophilia, Von Willebrand disease, etc.)
 - Unstable diabetes mellitus
 - Collapse and shock
 - Stroke/Embolism
 - Cardiac infarction within the last 3 months
 - Undefined coma status
 - Pregnancy (positive pregnancy test) prior to enrollment in the study for females of child-bearing potential
 - Females of child-bearing potential who are unwilling to use birth control during study participation
2. Parental decision to forego the use of Omegaven®
3. Known fish or egg allergy
4. Pregnancy
5. Causes of liver disease other than PNAC

B. Withdrawal Criteria

1. Decision of an assenting minor/adult subject or parent/guardian to withdraw from the study*
2. Anaphylaxis
3. Evidence of spur cell anemia.
4. Increasing anemia (hemoglobin < 7 g/dL) in the absence of gastrointestinal bleeding.
5. Mucosal bleeding or bleeding from IV insertion sites requiring transfusion.
6. Reproducible priapism associated temporally with the infusion
7. Mucosal bleeding associated with abnormal platelet function
8. Bowel adaptation such that patient can either come off TPN or such that enteral fat can meet the patient's nutritional requirements
9. Patient undergoes liver transplantation
10. Pregnancy
11. Patient is lost to follow up

* If an assenting minor chooses to withdraw from the study early, even if the parent wants the child to participate, the child will have their wishes respected.

C. Stopping Rules

If two subjects develop the same grade-3 adverse event (including liver function tests, Protocol – Compassionate Use of a Fish Oil-derived Intravenous Fat Emulsion (Omegaven®) to Reverse Parenteral Nutrition (PN) Induced Cholestasis

coagulation profile, and platelet count) related to the study medication that is irreversible upon de-escalation (does not reverse after 10 days) or upon discontinuation of the study drug, or any subject develops a related grade-4 adverse event, these events will be the cause for termination of the study.

D. Monitoring for toxicity due to Omegaven®

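### Historical controls are given neither the subjects' entry criteria nor a start date, so the only between-group efficacy comparison is open to selection and clock bias of unknown direction and size

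*Combined protocol and SAP*

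**What the plan says.** Section X states the comparison: "We will compare the group receiving Omegaven® with historical controls from our internal registry". Section XIII names the second analysis population as "historical controls from our internal registry who have demonstrated cholestasis while on Intralipid". Neither section adds a bilirubin level, a duration, a lipid dose, exclusions, a calendar period or a start date for controls, and neither refers to another section for them.

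Subjects are chosen far more narrowly. Section IX.A requires a "conjugated or direct bilirubin of ≥ 3 mg/dl for more than 4 weeks", with other causes of cholestasis reasonably excluded. It also requires that cutting soy lipid to an average below 1.2 g/kg/day "has failed to reduce the conjugated or direct bilirubin within ≥ 30 days of implementation". The exclusions add "Causes of liver disease other than PNAC".

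The subjects' clock is only implied: Section X describes the expected course "from the inception of Omegaven® therapy". Section XIII plans Kaplan-Meier curves, crude and adjusted Cox hazard ratios and a 0.05 significance threshold. Its sample size of 19 + 19 takes 10% resolution within 8 weeks for registry controls and about 50% for Omegaven. It also plans paired t-tests, and the power reference (reference 11) concerns matched case-control studies.

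**The concern.** A Kaplan-Meier or Cox comparison with external controls can be read as a treatment effect only if both groups could have entered the study and are timed from the same stage of disease. The plan secures neither.

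Its own text shows why this matters. Section X says: "The time to normalization will vary according to each patient's baseline conjugated or direct bilirubin level". Controls have no baseline requirement. The Background reports that reducing lipid helps some infants. Subjects are selected because that reduction failed, and controls are not.

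Every primary and secondary between-group efficacy comparison uses these controls. Without common eligibility and a common clock, a difference between the curves cannot be attributed to Omegaven, and a real effect could be hidden. Control selection and index dates could also be settled after the registry outcomes are known. Each subject's own bilirubin course can still be reported without controls.

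**Working it through.** **1. The two groups side by side**

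| Feature | Omegaven subjects (IX.A, X) | Controls (X, XIII) |
|---|---|---|
| Direct bilirubin | at least 3 mg/dl | cholestasis, no level |
| Duration | more than 4 weeks | not stated |
| Failed soy-lipid reduction | over at least 30 days | not stated |
| Other liver disease | excluded | not stated |
| Time zero | implied: start of Omegaven | not stated |
| Matching factors, covariates | none named | none named |

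**2. The plan's own sample size**

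Inputs from Section XIII are 10% and 50% at 8 weeks and alpha 0.05 (two-sided assumed). The stated beta of 0.80 is read as power of 0.80. The usual two-proportion formula, with mean rate 0.30, gives

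n = [1.96 × √(2 × 0.30 × 0.70) + 0.842 × √(0.10 × 0.90 + 0.50 × 0.50)]² / 0.40² = 19.4 per group.

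The arcsine formula gives 18.3, which rounds up to 19. A matched-pair formula gives 22.0 to 17.6 pairs for within-pair correlation of 0 to 0.3. The stated 19 + 19 is reproduced, so the arithmetic is not at fault. What is not established is that the 10% belongs to children who meet the entry criteria.

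**3. Sensitivity to the control rate (illustration)**

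Exact two-sided power at 0.05, with 50% on Omegaven, by enumeration of both binomials (Fisher / uncorrected chi-square). Control rates other than 10% are assumed.

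| Control rate | 19 vs 19 | 25 vs 25 |
|---|---|---|
| 5% | 87% / 93% | 95% / 98% |
| 10% | 71% / 82% | 83% / 91% |
| 15% | 54% / 68% | 68% / 79% |
| 20% | 40% / 53% | 51% / 64% |

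These figures show dependence on the 10%. They do not measure bias.

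**4. Why the direction is open**

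- *Against Omegaven.* If controls are counted from onset, a child who resolves in the first 4 weeks counts as a control event but could never have become a subject. Milder controls would act the same way.
- *In favour of Omegaven.* Suppose instead that control time includes a 30-day (4.29-week) lead-in during which no control can resolve, with constant hazard after it. An observed 10% at 8 weeks then arises in 8 − 4.29 = 3.71 weeks, and the aligned rate is 1 − 0.90^(8/3.71) = 20.3%. If the drug were inert, comparable untreated children truly resolved at 20%, and controls showed 10%, then 25 vs 25 would give a significant result favouring Omegaven 8.5% (Fisher) or 17.2% (chi-square) of the time, against a nominal 2.5%.

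Both are assumed scenarios. The documents do not say which clock would be used.

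**5. Baseline, and the 50% rate**

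Section X expects about 8 weeks without a fall on Omegaven, then about 1 mg/dl per week. Reaching 1 mg/dl takes 8 + (3 − 1) = 10 weeks from 3 mg/dl and 8 + (7 − 1) = 14 weeks from 7 mg/dl. No rate of fall on Intralipid is given, so this shows that baseline matters but cannot size an imbalance. It also means that nobody entering at 3 mg/dl or more would have resolved by 8 weeks, which does not fit the 50% at 8 weeks in Section XIII.

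**The case against.** **Matching may have been intended.** The paired t-tests and the matched-study power reference point that way. This stands as a hint. No matching factor or index date is stated, and the paired tests may be within-subject.

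**The adjusted Cox model may deal with it.** It is a partial safeguard. No covariate is named, and adjustment cannot repair an undefined origin or include children who could never have been eligible on equal terms.

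**The registry may be described elsewhere.** Parts of the Background and the text after the Data Management heading were not available, so control criteria there cannot be ruled out. This stands as a limit on certainty. Sections X and XIII refer to no such text.

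**This is compassionate use.** Entry continues even if efficacy has been shown, so no enrolment decision depends on the p value. That is correct, but the protocol still plans and powers a controlled comparison.

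Stronger readings are tempting but not supported:

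- A reader might infer that the comparison is biased towards Omegaven. The documents do not give the direction.
- A reader might infer that controls received unreduced Intralipid, or were timed from onset. Neither is stated.
- A reader might take "this protocol will call for even stricter inclusion criteria" as evidence that subjects are sicker than controls. That sentence compares this protocol with protocol 2009-1041, not with the registry.
- A reader might treat the power figures, or the 4-week qualifying period set against the 8-week horizon, as the size of the bias. They are illustrations.

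**Conclusion.** The concern holds for the text available. Controls need only have had cholestasis on Intralipid, while subjects pass severity, duration, failed-reduction and exclusion filters. Controls have no time zero. The only between-group efficacy comparison is therefore open to selection and clock bias of unknown direction and size, and the 10% control rate is not shown to apply to eligible children.

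The 19 + 19 arithmetic itself is sound. The one quantified consequence is conditional: if the control rate in a comparable set were 20% instead of 10%, power with 25 per group would fall from 83% / 91% to 51% / 64% (Fisher / chi-square, 50% on Omegaven). At 5% it would rise to 95% / 98%. This should be settled before any between-group result is produced, because the curves could not otherwise be interpreted as a drug effect.

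**What to change.** In Sections X and XIII:

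1. **Eligibility.** Restrict controls to registry patients who meet inclusion criteria 1 to 4 and the applicable exclusions, as far as records allow. Report their number and calendar period, and say which criteria (for example lipid dose for criterion 4) cannot be confirmed.
2. **One clock.** Start subjects at first Omegaven dose. Give each control an index date at the same time since first meeting criteria 3 and 4, while still on Intralipid and unresolved. Alternatively, start both groups when criteria 3 and 4 are first both met, with subjects entering the risk set at first dose so that the wait is not counted as treated time.
3. **Rates and power.** Re-derive the control rate in the restricted set on that clock. Check that the 50% Omegaven rate is on the same clock, and reconcile it with Section X's roughly 8 weeks without a fall. Restate power for the controls actually available.
4. **Adjustment.** Name baseline direct bilirubin as the covariate in the Cox model and keep any others very few. At the plan's rates, 25 subjects and 19 controls give about 0.50 × 25 + 0.10 × 19 = 14 events by 8 weeks.

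The cost is protocol wording, chart review and fewer qualifying controls. Stated power may become less favourable: at a 10% control rate, 25 subjects against 15 controls gives 73% / 81%, about the same as 19 vs 19, but against 10 controls it gives 55% / 64%.
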